6. COLLECTION OF STUDY VARIABLES

6.1 Recording of data

The Rave Web Based Data Capture (WBDC) system will be used for data collection and query handling. The investigator will ensure that data are recorded on the electronic CRFs as specified in the study protocol and in accordance with the instructions provided.

The investigator ensures the accuracy, completeness, legibility and timeliness of the data recorded and of the provision of answers to data queries according to the Clinical Study Agreement.

6.2 Data collection and enrolment

A study initiation visit must be conducted at the centre prior to the commencement of any study activities requiring informed consent (ie, any invasive screening tests).

A schedule for the tests and evaluations to be conducted in this study is contained in this Section 6.2 and [Table 2](#).

6.2.1 Screening

The following assessments and procedures should be performed within 28 days prior to first dose of study treatment unless otherwise stated.

- Signed informed consent for the study
- Date of birth, race and ethnicity
- Menopausal status; serum or urine pregnancy test for women of childbearing potential (within 28 days prior to study treatment start)
- Confirmation of pre-existing *BRCA1/2* mutation status
- Medical and surgical history
- Current and concomitant medications including previous cancer therapies
- Physical examination; ECOG performance status, vital signs (blood pressure and pulse, body temperature), body weight, and height. ECG (within 7 days prior to starting study treatment),.
- Haematology, clinical chemistry and urinalysis
- Tumour assessment (scans of the appropriate anatomical area applicable to the tumour under investigation and other sites as clinically indicated for assessment of disease by CT/MRI).

- Disease-specific blood biomarker (eg, CA-125 for ovarian, CA-15.3 for breast cancer PSA for prostate cancer etc) to be done within 7 days prior to starting study treatment.
- Adverse events (from time of consent)

The Principal investigator/sub-investigator should adhere to the study plan, procedures and perform tests/observations in accordance with the protocol.

6.2.2 On-trial assessments

Olaparib is self-administered by the patient twice daily as instructed continuously. The visit schedule is based on 28 days periods. Patients will attend the clinic on days 1 (1st day of treatment), 8, 15, 29, 57 and every 28 days thereafter and the following assessments will be performed at time points specified in the study schedule (see [Table 2](#))

- Physical examination, including ECOG performance status and vital signs every visit
- ECG on Day 57 only (ie, +8 weeks from starting study treatment)
- Haematology, clinical chemistry and urinalysis
- Serum or urine pregnancy test for women of childbearing potential (prior to treatment on day of first treatment)
- AEs/SAEs and concomitant medications
- Disease-specific tumour marker where appropriate (CA-125, CA15.3, PSA, CEA etc)
- Tumour assessments (scans of the appropriate anatomical area applicable to the tumour under investigation and other sites as clinically indicated for assessment of disease by CT/MRI) every 8 weeks after day 1. Note that, after 6 months on study treatment, the scanning frequency can be increased to every 12 weeks.

Patients will continue with olaparib until radiological objective disease progression by RECIST 1.1 or as long as in the investigator's opinion they are benefiting from treatment and they do not meet any other discontinuation criteria as outlined in Section 5.8. Once patients on olaparib have been discontinued from treatment, other treatment options will be at the discretion of the investigator.

Patients will be evaluated until objective disease progression by RECIST or commencement of subsequent anti-cancer therapy, as per the study schedule (see [Table 2](#)), and then followed for survival, regardless of whether study treatment is discontinued or delayed and/or protocol violations, unless they withdraw consent. A repeat scan is needed at the next scheduled tumour assessment (at least ≥ 4 weeks) for confirmation of a PR and CR by RECIST 1.1.

The imaging modalities used for RECIST assessment will be CT or MRI scans of the relevant sites clinically indicated for assessment of disease. Any other sites at which new disease is suspected should also be appropriately imaged. Clinical examination (eg, photography of skin lesions) is acceptable for assessment of non-target lesion response.

6.2.2.1 Disease-specific tumour marker plasma samples

All patients will supply plasma samples for tumour- specific marker assessment (if appropriate) at the beginning of each monthly visit prior to the patient receiving olaparib.

6.2.2.2 BRCA status

A patient's *BRCA* status must be known before enrolment into the study. Details of a patient's *BRCA1/2* mutation status will be collected on the eCRF.

6.2.3 Follow-up procedures

6.2.3.1 Treatment discontinuation visit

Patients should be discontinued from study treatment if any discontinuation criteria are fulfilled (see Section 5.8). The assessments to be carried out at the visit are detailed in the study schedule ([Table 2](#)).

6.2.3.2 Final follow up visit

A final follow-up visit should be conducted 30 days after the last dose of olaparib. Any serious and/or non-serious AEs ongoing at the time of the Discontinuation Visit or which have occurred during the defined 30-day follow-up period must be followed-up (in accordance with Sections 6.4.3, 6.4.4). Appropriate safety evaluations should be repeated and/or additional tests performed at any time when clinically indicated, or at the discretion of the investigator, until resolution, unless, in the investigator's opinion, the condition is unlikely to resolve due to the patient's underlying disease. If the patient is lost to follow-up, then this should be noted in the CRF.

6.2.3.3 Survival visit

Assessments for survival should be made every 8 weeks following objective disease progression. Survival information may be obtained via telephone contact with the patient, patient's family or by contact with the patient's current physician. The details of first and subsequent therapies for cancer after discontinuation of treatment will be collected. Survival data and subsequent therapy information will be collected up to the time of the primary analysis. In addition, patients should be contacted in the week following the data cut-off for the primary analysis to provide current survival data.

6.2.3.4 CT or MRI scans (RECIST 1.1)

Baseline and follow-up contrast-enhanced CT of the specific sites appropriate to the patient's tumour should be performed with other regions where clinically indicated for the adequate assessment of tumour burden. All baseline radiological tumour assessments must be performed no earlier than 28 days before the start of study treatment. Scans that were

performed as part of standard of care prior to signature of the informed consent form can be analysed for the purposes of the study if they were performed within the correct time frame and of sufficient quality. Subsequent tumour assessments according to RECIST should be performed at the end of every 8 weeks (+/-1 week) up to 6 months after starting treatment and then every 12 weeks thereafter according to the planned study schedule (see [Table 2](#)) up to objective progression by RECIST 1.1 ([Therasse et al 2000](#)). Any other sites at which new disease is suspected should also be appropriately imaged. Patients must be followed until RECIST disease progression.

Tumour evaluations using CT/MRI according to RECIST will continue in the study until the data cut-off for the analysis. At this point investigators will be notified that CT/MRI for study purposes are no longer required.

6.3 Efficacy

6.3.1 Efficacy variable

Table 4 Efficacy and Variables

Objective	Variable
To assess the efficacy of oral olaparib in patients with advanced cancer who have a confirmed genetic BRCA1 and/or BRCA2 mutation, by assessment of tumour response	Tumour Response Rate
To assess the efficacy of oral olaparib in patients with advanced cancer who have a confirmed genetic BRCA1 and/or BRCA2 mutation, by assessment of objective response rate (ORR), progression-free survival (PFS), overall survival (OS), duration of response (DOR) and disease control rate (DCR)	Objective response rate (ORR) Progression-free survival Overall survival Duration of response Disease control rate

6.3.2 Tumour Evaluation

RECIST 1.1 criteria will be used to assess patient response to treatment by determining tumour response, progression-free survival (PFS) times, objective response rates (ORR), duration of response (DOR) and disease control rate (DCR). The RECIST 1.1 guidelines for measurable, non-measurable, target and non-target lesions and the objective tumour response criteria (complete response, partial response, stable disease or progression of disease) are presented in [Appendix C](#).

The methods of assessment of tumour burden used at baseline -CT or MRI scans of neck, chest, abdomen, pelvis as appropriate to the tumour type under investigation - must be used at each subsequent follow-up assessment.

Following the baseline assessment, efficacy for all patients will be assessed by objective tumour assessments every 8 weeks \pm 1 week up to 6 months after starting study treatment and then every 12 weeks thereafter until objective disease progression as defined by RECIST 1.1.

If a patient discontinues treatment (and does not receive subsequent cancer therapy) prior to progression then the patient should still continue to be followed until objective disease progression as defined by RECIST 1.1.

For patients with measurable disease at baseline, categorisation of objective tumour response assessment will be based on the RECIST 1.1 criteria of response: CR (complete response), PR (partial response), SD (stable disease) and PD (progression of disease). Target lesion (TL) progression will be calculated in comparison to when the tumour burden was at a minimum (ie, smallest sum of diameters previously recorded on study). In the absence of progression, tumour response (CR, PR, SD) will be calculated in comparison to the baseline tumour measurements obtained before starting treatment.

For patients with non-measurable disease only at baseline, categorisation of objective tumour response assessment will be based on the RECIST 1.1 criteria of response: CR, PD and Non-CR/Non-PD.

If the investigator is in doubt as to whether progression has occurred, particularly with response to NTL (non-target lesion) or the appearance of a new lesion, it is advisable to continue treatment until the next scheduled assessment or sooner if clinically indicated and reassess the patient's status. If repeat scans confirm progression, then the date of the initial scan should be declared as the date of progression.

To achieve 'unequivocal progression' on the basis of non-target disease, there must be an overall level of substantial worsening in non-target disease such that, even in presence of SD or PR in target disease, the overall tumour burden has increased sufficiently to merit discontinuation of therapy. A modest 'increase' in the size of one or more non-target lesions is usually not sufficient to qualify for unequivocal progression status.

Following progression, patients should continue to be followed up for survival every 8 weeks as outlined in the study plan.

The analysis for this study will be based on the tumour assessments recorded on the CRF.

6.4 Safety

The Principal investigator is responsible for ensuring that all staff involved in the study is familiar with the content of this section.

6.4.1 Definition of adverse events

An adverse event is the development of an undesirable medical condition or the deterioration of a pre-existing medical condition following or during exposure to a pharmaceutical product, whether or not considered causally related to the product. An undesirable medical condition can be symptoms (eg, nausea, chest pain), signs (eg, tachycardia, enlarged liver) or the abnormal results of an investigation (eg, laboratory findings, electrocardiogram). In clinical studies, an AE can include an undesirable medical condition occurring at any time, including run-in or washout periods, even if no study treatment has been administered.

For cases where it could be suspected that a tissue-derived medicine has been contaminated by a pathogen, information about any of the above conditions (including infection) should be collected.

The term AE is used to include both serious and non-serious AEs.

6.4.2 Definitions of serious adverse event

A serious adverse event is an AE occurring during any study phase (ie, screening, run-in, treatment, washout, follow-up), at any dose of the study drugs that fulfils one or more of the following criteria:

- Results in death
- Is immediately life-threatening
- Requires in-patient hospitalisation or prolongation of existing hospitalisation
- Results in persistent or significant disability or incapacity
- Is a congenital abnormality or birth defect
- Is an important medical event that may jeopardise the patient or may require medical intervention to prevent one of the outcomes listed above.

For further guidance on the definition of a SAE, see [Appendix B](#) to the Clinical Study Protocol.

6.4.3 Recording of adverse events

Time period for collection of adverse events

Adverse Events will be collected from time of signed informed consent throughout the treatment period and up to and including the 30-day follow-up period.

SAEs will be recorded from the time of informed consent.

Follow-up of unresolved adverse events

Any AEs/SAEs that are unresolved at the patient's last AE assessment (ie, 30 day follow-up visit) in the study are followed up by the investigator for as long as medically indicated (see section [5.8.1](#)). AstraZeneca retains the right to request additional information for any patient with ongoing AE(s)/SAE(s) at the end of the study, if judged necessary.

Post-follow-up adverse events

After study treatment completion (ie, after any scheduled post-treatment follow-up period has ended) there is no obligation to actively report information on new AEs or SAEs occurring in former study patients. This includes new AEs/SAEs in patients still being followed up for

survival but who have completed the post treatment follow up period (30days). If an investigator learns of any SAEs, including death, at any time after a patient has completed the study, and he/she considers there is a reasonable possibility that the event is causally related to the investigational product, the investigator should notify AstraZeneca Patient Safety.

If patients who are gaining clinical benefit are allowed to continue study treatment post-data cut-off and / or post-study completion then as a minimum all SAEs must continue to be collected and reported to Patient Safety within the usual timeframe (section 6.4.4).

Variables

The following variables will be collect for each AE;

- AE (verbatim)
- the date and time when the AE started and stopped
- the maximum NCICTCAE grade attained
- whether the AE is serious or not
- investigator causality rating against the Investigational Product (yes or no) and study procedures/other medications
- action taken with regard to investigational product
- AE caused patient's withdrawal from study treatment (yes or no
- outcome.

In addition, the following variables will be collected for SAEs:

- Date AE met criteria for serious AE
- Date investigator became aware of serious AE
- AE is serious due to
- Date of hospitalisation
- Date of discharge
- Probable cause of death
- Date of death
- Autopsy performed

- Description of AE

Severity of AE

The grading scales found in the revised National Cancer Institute CTCAE version 3.0 will be utilized for all events with an assigned CTCAE grading. For those events without assigned CTCAE grades, the recommendation is the CTCAE criteria that convert mild, moderate and severe events into CTCAE grades should be used.

A copy of the CTCAE version can be downloaded from the Cancer Therapy Evaluation Program website (<http://ctep.cancer.gov>)

For each episode, the highest severity grade attained should be reported.

It is important to distinguish between serious and severe AEs. Severity is a measure of intensity whereas seriousness is defined by the criteria in Section 6.4.2. An AE of severe intensity need not necessarily be considered serious. For example, nausea that persists for several hours may be considered severe nausea, but not a SAE. On the other hand, a stroke that results in only a limited degree of disability may be considered a mild stroke but would be an SAE.

Causality collection

The investigator will assess causal relationship between the study medication and each adverse event, and answer “yes” or “no” to the question “Do you consider that there is a reasonable possibility that the event may have been caused by olaparib?”

Causal relationship will also be assessed for other medication and study procedures. Note that for AEs that could be associated with any study procedure the causal relationship is implied as “yes”.

A guide to the interpretation of the causality question is found in [Appendix B](#) to the Clinical Study Protocol.

Adverse Events based on signs and symptoms

All AEs spontaneously reported by the patient or reported in response to the open question from the study personnel: “Have you had any health problems since the previous visit?” or revealed by observation will be collected and recorded in the eCRF. When collecting AEs, the recording of diagnoses is preferred (when possible) to recording a list of signs and symptoms. However, if a diagnosis is known and there are other signs or symptoms that are not generally part of the diagnosis, the diagnosis and each sign or symptom will be recorded separately.

Adverse Events based on examinations and tests

The results from protocol-mandated laboratory tests and vital signs will be summarised in the clinical study report (CSR). Deterioration as compared to baseline in protocol-mandated

laboratory values, vital signs and other safety variables should therefore only be reported as AEs if they fulfil any of the SAE criteria or are the reason for discontinuation of treatment with olaparib.

If deterioration in a laboratory value/vital sign/ECG is associated with clinical signs and symptoms, the sign or symptom will be reported as an AE and the associated laboratory result/vital sign/ECG will be considered as additional information. Wherever possible the reporting investigator uses the clinical, rather than the laboratory term (eg, anaemia versus low haemoglobin value). In the absence of clinical signs or symptoms, clinically relevant deteriorations in non-mandated parameters should be reported as AE(s).

Deterioration of a laboratory value, which is unequivocally due to disease progression, should not be reported as an AE/SAE.

Any new or aggravated clinically relevant abnormal medical finding at a physical examination as compared with the baseline assessment will be reported as an AE.

Disease progression

Disease progression can be considered as a worsening of a patient's condition attributable to the disease for which the investigational product(s) is being studied. It may be an increase in the severity of the disease under study (DUS) and/or an increase in the symptoms of the disease. Expected progression of the patient's cancer and/or expected progression of signs and symptoms of the cancer, unless more severe in intensity or more frequent than expected for the patient's condition, should be considered as disease progression and not as an AE. Any events that are unequivocally due to disease progression should not be reported as an AE during the study.

New cancers

The development of a new primary cancer should be regarded as an AE and will generally meet at least one of the serious criteria (see Section 6.4.2). New primary cancers are those that are not the primary reason for the administration of the study treatment and have developed after the inclusion of the patient into the study. They do not include metastases of the original cancer. Symptoms of metastasis or the metastasis itself should not be reported as an AE/SAE, as they are considered to be disease progression.

Lack of efficacy

When there is deterioration in the condition for which the study treatment(s) is being used (patients with advanced cancers who have a confirmed genetic *BRCA1* and/or *BRCA2* mutation), there may be uncertainty as to whether this is lack of efficacy or an AE. In such cases, unless the Sponsor or the reporting physician considers that the study treatment contributed to the deterioration of the condition, or local regulations state to the contrary, the deterioration should be considered to be a lack of efficacy and not an AE.

Deaths

All deaths that occur during the study, or within the protocol-defined 30-day post-study follow-up period after the administration of the last dose of study treatment, must be reported as follows:

- Death clearly the result of disease progression should be reported to the study monitor at the next monitoring visit and should be documented in the eCRF but should not be reported as an SAE.
- Where death is not due (or not clearly due) to progression of the DUS, the AE causing the death must be reported to the study monitor as a SAE within **24 hours** (see Section 6.4.4 for further details). The report should contain a comment regarding the co-involvement of progression of disease, if appropriate, and should assign main and contributory causes of death. This information can be captured in the 'death eCRF'.
- Deaths with an unknown cause should always be reported as a SAE. A post mortem maybe helpful in the assessment of the cause of death, and if performed a copy of the post-mortem results should be forwarded to AstraZeneca within the usual timeframes.

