1.1.9 Toxicology and safety pharmacology summary

Olaparib has been tested in a standard range of safety pharmacology studies eg, dog cardiovascular and respiratory function tests, and the rat Irwin test. There were no noticeable effects on the cardiovascular or respiratory parameters in the anaesthetised dog or any behavioural, autonomic or motor effects in the rat at the doses studied.

The toxicology studies indicate that the target organ of toxicity is the bone marrow.

Further information can be found in the current version of the olaparib IB.

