5.5.6 Management of toxicity of olaparib (monotherapy treatment)

Any toxicity observed during the course of the study should be managed by interruption of the dose if deemed appropriate by the investigator. Repeat dose interruptions are to be allowed as required, for a maximum of 4 weeks (28 days) on each occasion. Olaparib must be interrupted until the patient recovers completely or the toxicity reverts to National Cancer Institute (NCI) Common Terminology Criteria for Adverse Events (CTCAE version 3) grade 1 or less.

Where toxicity reoccurs following re-challenge with olaparib and where further dose interruptions are considered inadequate for management of toxicity, then the patient is to be considered for dose reduction or must permanently discontinue treatment with olaparib.

Treatment must be interrupted if any NCI-CTCAE grade 3 or 4 adverse event occurs which the investigator considers to be related to administration of olaparib. If this has not resolved to at least NCI-CTCAE grade 1 during the maximum 4 weeks (28 days) dose interruption period, and/or the patient has already undergone a maximum of 2 dose reductions already, (to a minimum dose of 100 mg bd), the patient must permanently discontinue treatment with olaparib. If toxicity is appropriately resolved, then the patient should restart treatment with olaparib, but with a 50% dose reduction according to [Table 3](#). If the event recurs with the same severity, treatment should be interrupted again and, on resolution, a further dose

reduction made. If, on restarting treatment, the event continues to occur, the patient must permanently discontinue olaparib.

An exception to the management of olaparib-related toxicity is the occurrence of leukopenia and/or anaemia. In this case, the AE should be managed as deemed appropriate by the investigator (growth factor, transfusions), without interruption in study drug or change in dose. However, growth factors must be discontinued once the AE has recovered to grade 1 or better. They may be resumed, if necessary, if leukopenia/anaemia develops again and discontinued once it recovers.

The dose of olaparib must not be adjusted under any other circumstances unless the AstraZeneca physician gives prior agreement. Once the dose of olaparib has been reduced under no account should it be re-escalated.

All dose reductions and interruptions (including any missed doses), and the reasons for the reductions/interruptions are to be recorded in the eCRF.

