6.4.5 Laboratory safety assessment

Blood samples for determination of clinical chemistry, haematology and coagulation will be taken at the times indicated in the Study Schedule (see [Table 2](#))

The following laboratory variables will be measured:

Full haematology assessments for safety (haemoglobin, red blood cells [RBC], platelets, mean corpuscular volume [MCV], mean corpuscular haemoglobin concentration [MCHC], mean corpuscular haemoglobin [MCH], white blood cells [WBC], differential white cell count and absolute neutrophil count should be performed at each visit and when clinically indicated. Coagulation [activated partial thromboplastin time {APTT} and international normalised ratio {INR}]) will be performed at baseline and if clinically indicated unless the patient is receiving warfarin.

Biochemistry assessments for safety (sodium, potassium, calcium, magnesium, glucose, creatinine, total bilirubin, gamma glutamyltransferase [GGT], alkaline phosphatase [ALP], aspartate transaminase [AST], alanine transaminase [ALT], urea or blood urea nitrogen [BUN], total protein, albumin, lactic dehydrogenase [LDH]) amylase and lipase will be performed.

Urinalysis by dipstick should be performed at baseline and then only if clinically indicated. Microscopic analysis should be performed by the hospital's local laboratory if required.

These tests will be performed by the hospital's local laboratory. Additional analyses may be performed if clinically indicated.

Any clinically significant abnormal laboratory values should be repeated as clinically indicated and recorded on the eCRF.

For blood volumes see Section [7.1](#)

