12.2.2.6 Safety

Assessment of safety will be based on the SAS population. For listings and summaries of changes from baseline, the latest available value pre-first dose of study treatment will be used.

All adverse events will be listed for each patient and summarised according to the system organ class (SOC) and preferred term assigned to the event using the Medical Dictionary for Regulatory Activities (MedDRA). AEs will be graded according to the National Cancer Institute Common Terminology Criteria for AEs. The CTCAE grade will be assigned by the investigator.

Any AEs occurring after the first dose of study treatment and within 30 days of the last dose of study treatment will be included in the AE summaries. AEs occurring before the first dose of study treatment or more than 30 days after the last dose of study treatment will not be included in AE summaries but will be included and identified in the patient listings.

Clinical chemistry, haematology and vital signs (pulse rate and blood pressure) data will be listed for each patient and summarised with descriptive statistics (mean, standard deviation, median, minimum, maximum, number of patients) by scheduled visit. Both absolute values and changes from baseline will be presented. ECG results (normal and abnormal) will be summarised by visit using frequency counts and percentage of patients for each treatment group.

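### Section 6.4.3 keeps asymptomatic, non-serious grade 3-4 laboratory falls out of the AE record even when they change the dose, and does not fit 6.4.1, 6.4.7.1 or 5.5.6

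*Protocol*

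**What the plan says.** Section 6.4.3, under the heading on examinations and tests, limits AE reporting for deteriorations in protocol-mandated measurements: "laboratory values, vital signs and other safety variables should therefore only be reported as AEs if they fulfil any of the SAE criteria". A second ground follows: "or are the reason for discontinuation of treatment with olaparib". If the change comes with symptoms, "the sign or symptom will be reported as an AE and the associated laboratory result/vital sign/ECG will be considered as additional information". The reason given is that mandated laboratory and vital-sign results will be summarised separately in the study report.

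Haematology is protocol-mandated. Section 6.4.5 requires it at each visit: "Full haematology assessments for safety (haemoglobin, red blood cells [RBC], platelets", white cells, differential and neutrophil count.

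Section 12.2.2.6 says how these data are presented. They are listed by patient and "summarised with descriptive statistics (mean, standard deviation, median, minimum, maximum, number of patients) by scheduled visit", for absolute values and changes from baseline. Section 11.2 adds that values outside the reference range will be identified, and 11.2.1 adds a sponsor expert's review of laboratory data for other significant AEs.

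Section 5.5.6 makes interruption mandatory on an adverse event: "Treatment must be interrupted if any NCI-CTCAE grade 3 or 4 adverse event occurs which the investigator considers to be related" to olaparib. The reduction steps in Table 3 are also worded in terms of related grade 3 or 4 SAEs or AEs. Section 1.1.9 states that "the target organ of toxicity is the bone marrow".

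**The concern.** Safety and tolerability is a stated objective (2.3), marrow is the stated target organ, and 1.1.10 already reports thrombocytopenia that is sometimes grade 3 or 4. In such a trial, the toxicity most likely to change the dose is a laboratory finding. The 6.4.3 rule covers serious cases and cases that end treatment, but not those that lead to interruption or dose reduction.

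Two things are at stake. The graded AE tables would under-record haematological toxicity, and the details collected only for AEs would not exist for those cases. Sites would also be working from passages that use the term adverse event in different ways, including in the passage that governs interruption and reduction.

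**Working it through.** No figure in the protocol is at issue. The check is to follow a grade 3-4 fall in a mandated laboratory value through the sections.

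**Step 1: is it recorded as an AE?**

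| Type of grade 3-4 fall | AE entry under 6.4.3 | Where else it appears |
|---|---|---|
| Meets an SAE criterion (Appendix B gives neutropenia or anaemia needing transfusion as an example) | Yes | Laboratory listing and summaries |
| Reason for stopping olaparib | Yes | Laboratory listing and summaries |
| Symptomatic, not serious | The sign or symptom is the AE; the laboratory value is additional information | Laboratory listing and summaries |
| Asymptomatic, not serious, leads to interruption or reduction | No | Laboratory listing and summaries; dose change and its reason in the eCRF (5.5.6) |
| Asymptomatic, not serious, no dose change | No | Laboratory listing and summaries |

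The gap is the last two rows. The fourth matters most, because the event was important enough to change treatment.

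**Step 2: what is lost without an AE entry?** Section 6.4.3 lists what is collected per AE: start and stop, maximum CTCAE grade, seriousness, investigator causality, action taken with olaparib, whether it led to withdrawal from treatment, and outcome. Grade can be derived later from laboratory values. The dose change and its reason are recorded separately. Investigator causality and AE outcome have no other stated source.

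**Step 3: does the laboratory presentation replace the AE count?** The mean, SD, median, minimum, maximum and number of patients by visit do not say how many patients reached grade 3 or 4. The minimum shows the worst single value at a visit, not a number of patients. Section 11.2 flags against reference ranges, not CTCAE grades. The review in 11.2.1 is by judgement and requires no incidence. The listings hold the values but give no count. So no stated output requires a count by CTCAE grade.

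**Step 4: do the sections agree on what an AE is?**
- Section 6.4.1 defines an AE to include abnormal results of investigations and names laboratory findings. Section 6.4.3 tells sites not to report most of them.
- Section 6.4.7.1 has any clinically significant ECG abnormality recorded as an AE. Section 6.4.3 restricts mandated safety variables to serious or treatment-ending cases.
- Within 6.4.3, an asymptomatic, clinically relevant deterioration in a non-mandated parameter is an AE, while the same kind of change in mandated platelets is not.
- Section 5.5.6 refers to leukopenia or anaemia as an AE and follows its recovery to grade 1. Under 6.4.3 it may have no AE entry.

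**Step 5: is the trigger in 5.5.6 met?** Take an asymptomatic, non-serious, related grade 3-4 platelet fall. By the definition in 6.4.1 it is an adverse event, and the trigger is met. If a site takes adverse event to mean what 6.4.3 allows to be reported, it is not. Both readings are open. Leukopenia and anaemia are exempt from interruption and dose change under 5.5.6, so the ambiguity bears mainly on thrombocytopenia, and on neutropenia only if that is not read as leukopenia.

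**The case against.** The strongest reply has four parts.

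*Reporting is not definition.* Section 6.4.3 limits what is reported and does not redefine an AE. The trigger in 5.5.6 speaks of an event occurring, so 6.4.1 can satisfy it. Section 5.5.6 also allows interruption for any toxicity at the investigator's discretion. This stands to the extent that a reader might infer that the interruption rule simply fails for laboratory events. The protocol does not support that; it supports only that the rule can be read two ways.

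*The laboratory data are not hidden.* A reader might infer that laboratory results are reported only as means, that grade 3-4 marrow toxicity is counted nowhere, or that the trial could not report it. None of these holds. Minimum, maximum and listings are planned, out-of-range values are flagged, and marked haematological abnormalities are an example in the expert review. Serious and treatment-ending cases are AEs, and grades can be derived from values already collected.

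*A grade table belongs in the statistical analysis plan.* That plan is not shown and may contain one. This stands: the missing table alone would be no finding. But an analysis plan cannot supply causality and outcome that were never collected, nor align what sites read in different protocol sections.

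*It is a deliberate choice in an exploratory study.* Reporting laboratory results separately has a stated reason, and the primary endpoint is unaffected. This lowers the severity. It does not explain why a laboratory event that changes the dose needs no AE entry.

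**Conclusion.** The point holds in a limited form. As written, 6.4.3 leaves asymptomatic, non-serious grade 3-4 cytopenias out of the graded AE tables and without AE-level causality or outcome, even when they lead to interruption or dose reduction. The stated laboratory outputs require no count by grade. The rule also conflicts with 6.4.1 and 6.4.7.1 and makes the trigger in 5.5.6 and Table 3 ambiguous, mainly for thrombocytopenia.

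The size cannot be put in patients. The protocol gives no incidence of grade 3-4 cytopenia and no share that is asymptomatic and non-serious, so any number out of the planned 150 would be an assumption. The conclusion rests on sites following 6.4.3 literally; sites that work from 6.4.1 would record more.

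This is worth correcting because AE details not collected at the time may be lost, but it is not critical to the trial's main result.

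**What to change.** 1. In 6.4.3, add to the AE reporting criteria any deterioration in a protocol-mandated laboratory value that is CTCAE grade 3 or higher, or that leads to interruption or dose reduction.
2. As a supporting change, state in 12.2.2.6 a summary of worst on-treatment CTCAE grade and of shift from baseline for laboratory values. The data are already collected. If the statistical analysis plan already has this, a cross-reference is enough.
3. Reconcile 6.4.1, 6.4.3, 6.4.7.1 and 5.5.6 with Table 3, so that sites have one reading of whether a graded laboratory value counts as an adverse event. Which clinical rule should apply is for the sponsor's clinicians; none is proposed here.

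The cost is a short amendment, a reminder to sites and two tables. There will be more AE entries, and reported AE rates will look less favourable than under the current rule.
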